1.0 Protocol synopsis

Title	A moulting starting level at a monday of warden alwater wards mixed		
Title	A multi-centre, practice-level, stepped wedge cluster randomized, controlled trial to compare point-of-care HCV RNA testing, dried blood spot testing, and standard of care to enhance treatment uptake among people with HCV who have recently injected drugs attending needle and syringe programs: the TEMPO study		
Protocol registration no.	NCT04014179		
Background and rationale	Viral hepatitis is the 7 th leading cause of mortality globally, having surpassed the number of annual deaths due to HIV, malaria, and tuberculosis¹. Globally, 71 million people are living with HCV virus (HCV), with 6.1 million having recently injected drugs², and an additional burden among former people who inject drugs (PWID). In Australia, the majority of existing (80%) and new (90% of 9,000 annually) cases are in PWID³,⁴. The advent of simple, well-tolerated, direct-acting antiviral (DAA) HCV therapies with cure rates >95% is one of the most exciting medical advances in decades⁵. Successful therapy leads to improved quality of life and reduced morbidity/mortality⁶, providing an opportunity to reverse the rising burden of advanced liver disease.		
	The World Health Organization (WHO) has set a goal to eliminate HCV as a global public health threat by 2030, with targets to increase HCV diagnoses and treatment, and reduce new infections and liver-related mortality ⁷ . However, among the 71 million people with HCV worldwide, less than 20% have been diagnosed and less than 10% have received treatment ⁸ . In Australia, HCV DAA treatment uptake initially exceeded expectations (2016: 32,400 treated; 14% with HCV). But, the number of people initiating therapy has continued to decline (2017: 21,370; 2017: ~2,000/month; 2018: ~1,400/month). Improving HCV testing and treatment to reduce disease burden is a key aim of global and national HCV strategies ^{9,10} .		
	Globally, HCV testing and diagnosis remains inadequate ¹¹ . Current testing algorithms involve detection of HCV antibodies to confirm exposure, followed by HCV RNA testing to detect active infection. This two-step pathway requires up to 5 visits to practitioners and off-site phlebotomists, leading to a drop-off in those receiving a diagnosis of active infection ¹² . Standard of care HCV testing is also limited by a lack of on-site phlebotomists (requiring off-site referral) and poor venous access (a major problem among people who inject drugs). In Australia, 81% have had an antibody-based HCV diagnosis, but only 47% have been tested for active infection ¹² . As highlighted in the 4th National HCV Strategy , a Priority Action is to "improve referral and access to high quality support services at the time of diagnosis for people with HCV to initiate a pathway to care".		
	In a systematic review of interventions to improve HCV care among PWID led by our group ¹³ , key interventions to enhance HCV testing		

(on-site testing; and dried blood spot testing), linkage to care (facilitated referral for HCV assessment) and treatment (integrated HCV care) were identified. Studies were limited by small sample sizes, and the lack of randomized controlled trials or comparative studies in the DAA era. Well-designed studies evaluating interventions to enhance HCV testing/treatment among PWID are needed.

Dried blood spot testing can enhance HCV testing and linkage to care^{13,14}. Benefits of dried blood spots include: 1) avoiding the need for phlebotomy; 2) enables testing for HCV antibodies (exposure) and RNA (active infection); 3) easy to transport/store; 4) can test for other viruses (e.g. HIV); 5) sample collection can be performed by peers or self-collection¹¹. Also, dried blood spot testing has excellent sensitivity and specificity for the detection of active HCV ¹⁵.

Point-of-care HCV testing has also been demonstrated to increase testing and linkage to care¹⁴. Our group led the first evaluation of a finger-stick point-of-care HCV RNA assay^{16,17} as part of a clinical observational study in drug treatment clinics and needle and syringe programs (NSPs), enabling same-day diagnosis of active infection (HCV RNA) in one hour (sensitivity and specificity, 100%)¹⁷. The findings have informed regulatory approval submissions in Europe and Australia. The next step is to translate this novel discovery into routine clinical practice. There is an unprecedented opportunity to evaluate whether finger-stick point-of-care HCV RNA testing could be integrated into routine practice to enhance HCV testing and treatment among PWID.

Settings for HCV care for PWID include hospitals, primary care, drug treatment clinics, and prisons¹⁸. But, there is a need to link less service-connected PWID to HCV care. In Australia, there is broad NSP access (3,627 NSPs; 98 primary sites)¹⁹ and PWID regularly attend NSPs to collect injecting equipment. NSPs offer an opportunity to engage with PWID who may not be engaged in health services. Further, on-site testing improves linkage to HCV treatment¹³. As highlighted in the *National HCV Strategy*, "Peer support programs offering education may improve engagement in HCV assessment/treatment²⁰" and "The role of peer educators to increase testing should be explored. Such services should be linked to peer-based drug-user organisations...and NSPs."

The TEMPO study will compare point-of-care HCV RNA testing, dried blood spot testing, and standard of care as strategies to enhance HCV treatment uptake among people with HCV and recent injecting drug use attending NSP services.

Study objectives

Primary objective

To compare the proportion of HCV RNA positive participants who initiate HCV treatment at 12 weeks following enrolment between those who receive point-of-care HCV RNA testing, dried blood spot testing, and standard of care.

Secondary objective(s)

Among those who receive point-of-care HCV RNA testing, dried blood spot testing, and standard of care:

- 1. To compare the time to HCV DAA treatment initiation among those who initiate treatment.
- 2. To compare the proportion of HCV RNA positive participants who initiate HCV DAA treatment at 24 weeks following enrolment.
- To compare the proportion of HCV RNA positive participants who initiate HCV DAA treatment at 12 months (52 weeks) following enrolment.
- 4. To compare the proportion of participants who complete HCV DAA treatment.
- 5. To compare the proportion of participants who achieve an SVR (defined as HCV RNA below the lower limit of quantitation at post treatment week 12).
- 6. To compare the proportion of participants who are HCV RNA negative at 12 weeks.
- 7. To compare the proportion of participants who are HCV RNA negative at 24 weeks.
- 8. To compare the proportion of participants who are HCV RNA negative at 12 months (52 weeks).
- 9. To evaluate the incidence of HCV reinfection following successful HCV therapy.
- 10. To compare the cost-effectiveness of these different testing strategies.

Participant population

It is anticipated that approximately 3,300 participants (assuming an HCV RNA prevalence of 20%) will be screened for HCV infection using either dried blood spot testing, point-of-care testing or standard of care testing.

Screening in the intervention arm will continue until a total of 220 HCV RNA positive participants (~20 participants per site) are enrolled in the intervention arm (either dried blood spot and point-of-care). In the delayed intervention arm, 220 HCV RNA positive participants (~20 participants per site) will be enrolled in the control (standard of care) phase and then clusters/sites will be switched to intervention (either dried blood spot and point-of-care) – at which screening will continue until a total of 220 HCV RNA positive participants (~20 participants per site) are enrolled. Hence a total of 660 HCV RNA positive participants.

Identification and inclusion criteria for clusters

NSPs must meet the following criteria to participate in the study:

- a. Be a primary NSP site, defined as, providing services to PWID staffed by specialist workers
- b. Have the capacity for on-site nursing support or externally, and HCV treatment provision
- c. Provide services to > 60 people per week.

Potential eligible NSP sites will be identified from existing service centres in Australia and will complete site feasibility assessment to ensure the inclusion criteria are met. NSP sites may have prior experience or are active in surveillance and clinical studies, but it is not mandatory to have clinical research experience.

Inclusion criteria for participants

Attendees of the NSP service are eligible for inclusion if the following criteria are met:

- a. Provided written informed consent
- b. ≥ 18 years of age
- c. Recent injecting drug use defined as self-reported use within the previous six months.

Exclusion criteria for participants

a. Is unable or unwilling to provide informed consent or abide by the requirements of the study.

Eligibility criteria for treatment

Participants who have a quantifiable HCV RNA will be assessed for treatment eligibility. Those in the point-of-care arm will be able to complete the treatment work-up on the day of HCV screening. Those in the control arm and dried blood spot arm will have treatment work-up as per standard of care once the HCV RNA test results are received from the laboratory.

Inclusion criteria for treatment

Participants are eligible for HCV DAA treatment if all of the following inclusion criteria are met:

- a. Quantifiable HCV RNA at screening
- b. An assessment of liver cirrhosis status is performed in the intervention arm, i.e. point-of-care and dried blood spot arm:
- If pathology is available to determine an APRI in the previous 12 months, and is <1.0, then a FibroScan is not required.

OR

- ii) If pathology is not available for APRI, and no FibroScan is available, then phlebotomy can be taken at baseline and treatment commenced. Once pathology is returned, if >1.0 then an ultrasound can be organised. In these cases (unknown stage of disease) would be preferable to use SOF/VEL, given standard duration.
- c. In the opinion of the Investigator, the participant is suitable for treatment within an NSP-based setting.

Exclusion criteria for treatment

	 a. In the opinion of the Investigator, any factors or reasons which could preclude management within an NSP-based setting 				
	b. Any clinically significant condition or history known to contraindicate the use of the prescribed DAA treatment medication or would not be suitable for management				
	within an NSP-based setting c. Any medication contraindicated to the prescribed HCV DAA treatment regimen (as detailed in the product				
	information)				
	d. HIV co-infection*				
	e. Active hepatitis B co-infection*f. Is female and is pregnant or breastfeeding.				
	1. Is lethate and is pregnant of breastieeding.				
	*Participants who meet all other eligibility criteria but have HIV of active hepatitis B co-infection can be eligible for treatment if the HCV treatment is co-managed with a specialist.				
Study design	HCV treatment is co-managed with a specialist. The study is a multi-centre, practice-level, stepped wedge cluster randomized controlled trial. The clusters will be primary needle syringe programs (which provide services to people who inject drugs and have capacity to provide HCV treatment) located in Australia. Twenty-two NSPs [the clusters] will be randomly allocated to receive the intervention immediately (11 clusters) versus standard of care with delayed intervention (11 clusters). The immediate intervention arm will be randomized 1:1 to receive point-of-care HCV RNA testing (5 or 6 clusters)* or HCV RNA testing from dried blood spots (5 or 6 clusters)*. The delayed intervention arm will have a period of standard of care (based on the number of enrolled participants) and switch to receiving the intervention. The delayed intervention arm will then be randomized 1:1 to receive point-of-care HCV RNA testing (5 or 6 clusters)*. As such, at the end of the study, there will be 11 clusters randomized to point-of-care HCV RNA testing or 11 clusters to HCV RNA testing from dried blood spots. *Based on randomisation, there will be 5 sites using point-of-care and 6 sites using dried blood spots, or vice versa with 6 sites using point-of-care				
Treatment of participants	and 5 sites using dried blood spots. At enrolment, participants will be referred for testing (standard of care), tested for HCV infection with dried blood spot, or tested with an HCV RNA point-of-care, depending on cluster randomisation.				
	Participants who are eligible for treatment will be prescribed an approved pan-genotypic DAA HCV treatment at the discretion of the Investigator. The dose, form, strength, regimen and duration of treatment will be as per the approved product information for the prescribed regimen.				
Study procedures	Refer to the Schedule of Assessments.				
Statistics	Hypothesis				
	Compared to standard of care, an intervention consisting of either dried blood spot testing or point-of-care HCV RNA testing will lead				

to an increased proportion who initiate HCV treatment at 12 weeks following enrolment among people with HCV who have recently injecting drug use attending NSP services.

Compared to dried blood spot testing, point-of-care HCV RNA testing will lead to an increased proportion who initiate HCV treatment at 12 weeks following enrolment among people with HCV who have recently injecting drug use attending NSP services.

Primary outcome

The proportion who initiate HCV treatment at 12 weeks from enrolment.

Sample size

Control versus intervention: The sample size for comparing control versus intervention was calculated by using a stepped wedge cluster randomized controlled trial design (two steps) accounting for estimates of outcomes in the control arm (p1), the average of intervention arms (p2), the mean cluster size (m), the intracluster correlation coefficient (ICC) for the proportion initiating treatment (rho), and study power. Given an HCV RNA prevalence of 20% (based on data from the Australian NSP survey), it is estimated that 100 participants will need to be screened to enable a mean cluster size (m) of 20 participants. For the comparison of control and intervention, we assumed 22 NSP sites/clusters (3,300 tested, 660 HCV RNA detectable), two steps, a mean cluster size (m) of 20 people who are HCV RNA positive, HCV treatment uptake of 10% over 12 weeks in the control group (p1), an intracluster correlation coefficient of ρ =0.05 (to provide a more conservative variation in treatment uptake) and 90% power. Under these assumptions, we are powered to detect a difference of HCV treatment uptake of 20% between control and intervention arms [e.g. 30% in intervention arm (p2)] with α =0.05.

Dried blood spot versus point-of-care HCV RNA testing: The sample size for comparing dried blood spot testing to point-of-care HCV RNA testing was calculated by using a cluster randomized controlled trial design accounting for estimates of outcomes in dried blood spot testing arm (p1) and the point-of-care HCV RNA testing arm (p2), the mean cluster size (m), the intracluster correlation coefficient (ICC) for the proportion initiating treatment (rho), and study power. Given an HCV RNA prevalence of 20% (based on data from the Australian NSP survey), it is estimated that 100 participants will need to be screened to enable a mean cluster size (m) of 20 participants. For the comparison of control and intervention, we assumed 22 NSP sites/clusters (3,300 tested, 660 HCV RNA detectable), a mean cluster size (m) of 20 people who are HCV RNA positive, HCV treatment uptake of 20% over 12 weeks in the dried blood spot testing (p1), an intracluster correlation coefficient of ρ=0.05 (to provide a more conservative variation in treatment uptake) and 90% power. Under these assumptions, we are powered to detect a difference of HCV treatment uptake of 25% between control and intervention arms [e.g. 45% in point-of-care HCV RNA testing arm (p2)] with α =0.05.

In the intervention and control arms, the total number tested will be 3,300 [total infected, n=660; total treated, n=165 (n=22 in the control arm, n=44 in the dried blood testing arm, and n=99 point-of-care HCV RNA testing arm)].

[figure not shown]
Randomisation

Clusters will be randomised using a computer-generated randomisation scheme, minimised based on cluster characteristics (geographic location and urban vs rural classification).

Statistical analysis

Analysis will follow the CONSORT guidelines for cluster randomised trials²¹. The analysis of the primary outcome will occur when all participants have completed 12 weeks of follow-up or have been permanently lost to follow-up. Participant and cluster flow will be summarised, showing the numbers of clusters and participants randomised and included, and numbers of participants across clusters who complete follow-up with a primary outcome. The primary endpoint will be the proportion of participants who initiate HCV treatment within 12 weeks. Participants who initiate HCV treatment will be traceable, so participants lost to follow-up before initiating HCV treatment will be included in Intention to Treat analyses as having not initiated treatment. Randomised groups will be compared using repeated measures logistic regression methods, clustered on site, fitted using GEE methods with robust standard errors. Secondary analyses will include the proportion linked to care, time to HCV treatment initiation, the proportion initiating HCV treatment by 24 weeks of follow-up, the proportion initiating HCV treatment by the end of follow-up, HCV treatment completion, and response to HCV treatment.

1.1 Study Flow Chart Study Flow Chart – Cluster/Site Level

Based on randomisation, there will be 5 sites using point-of-care and 6 sites using dried blood spots, or vice versa with 6 sites using point-of-care and 5 sites using dried blood spots.

DBS Research

[figure not shown]
Sample collection Questionnaires

1.2 Study Flow Chart - Participant Level

Intervention Arm On Treatment Visits Participants commencing treatment ONLY Clinical assessment as per standard of care **Screening Visit** Registration Post-enrolment Week 12* Post-enrolment Week 24* Post-enrolment 12 Months · HCV RNA via dried blood Quantifiable HCV RNA HCV RNA via dried blood · HCV RNA via dried blood spot Consent HCV RNA via dried ONLY spot or point-of-care spot or point-of-care or point-of-care Questionnaires blood spot or point- Questionnaires Questionnaires Treatment assessment *May coincide with on-treatment *May coincide with SVR12 visit for of-care Fibrosis assessment

ETR visit

Control Arm

• HIV Ab and HBsAg

patients on treatment

1.3 Participant Schedule of Assessments

1.3.1 Intervention Arm

	All participants	Participants with a quantifiable HCV RNA					
Study Visit	Screening	Registration	Follow-up Visit 1	Follow-up Visit 2	Follow-up Visit 3		
Study Weeks	0	0	12	24	52		
Visit Window (weeks, min to max)	0	N/A	10 to 14	14 to 34	34 to 56		
Informed consent	X						
Behavioural questionnaire (Screening version)	x						
Behavioural questionnaire (Follow-up version)			Х	х	х		
EQ-5D-5L	Х		X	X	Х		
Health economics questionnaire	х		Х	Х	х		
HCV RNA ¹	Х		X	X	Х		
HCV RNA result notification ²	X	Х					
HCV treatment work-up (as per standard of care) ³		х					
HIV serology		X ⁴					
HBV serology		X ⁴					
FibroScan® / APRI		X ⁵					
Research Samples	Research Samples						
Dried blood spot	Х	_			_		

Key	
1	HCV RNA via point-of-care or dried blood spot. Participants with a non-quantifiable and detected result are recommended for further testing for confirmation.
2	Point-of-care arm: HCV RNA result will be delivered on the same day of testing where possible. Dried blood spot arm: HCV RNA result will be delivered within two weeks of testing. Refer to section 10.2 for additional details.
3	Treatment work-up for enrolled participants with a quantifiable HCV RNA who wish to commence anti-HCV DAA therapy. To be conducted on day of the HCV RNA test where possible.
4	For participants with a quantifiable HCV RNA who initiate HCV treatment, their HIV and HBV status will be determined using rapid tests. Excluded for those with a recent known status.
5	Measure of liver cirrhosis by either a FibroScan (if available at site) or an APRI result from a phlebotomy for participants with a quantifiable HCV RNA who initiate HCV treatment.

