10.2 HCV RNA test notification

Participants at sites randomized to standard of care or dried blood spots will be notified once their results are returned from the testing laboratory whilst those at sites randomized to point-of-care will be notified of their results on the same day (where possible).

Negative results from dried blood spot HCV RNA testing will be delivered through a text message. Participants with a positive result from dried blood spot HCV testing will be notified through a text message to contact the study site team to facilitate the participant to return to the site for HCV RNA results and linkage to care. Positive HCV RNA results will be delivered in person by the site study team.

To facilitate participant notification of results, contact details (phone number and/or email, if available) will be collected through an electronic data capture system. Up to 3 secondary contact

^{**}At time of treatment initiation and excluded for those with a recent known status.

details (phone number and/or email) will be collected in case the study team cannot reach the study participant on their main contact details.

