10.5 Follow-up phase

All HCV RNA positive participants i.e., participants with a quantifiable HCV RNA in the intervention arm only will return for follow-up visits at 12 weeks, 24 weeks and 12 months (52 weeks) post-test. The following procedures will be conducted at follow-up visits:

- Follow-up behavioural questionnaire
- Health outcomes survey (EQ-5D-5L) and health economics questionnaire

- HCV RNA (either dried blood spot or point-of-care)
- Participant reimbursement

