14.2 Primary outcome

The proportion who initiate HCV treatment at 12 weeks from enrolment.

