14.5 Statistical analysis

Analysis will follow the CONSORT guidelines for cluster randomised trials²¹. The analysis of the primary outcome will occur when all participants have completed 12 weeks of follow-up or have been permanently lost to follow-up. Participant and cluster flow will be summarised, showing the numbers of clusters and participants randomised and included, and numbers of participants across clusters who complete follow-up with a primary outcome. The primary endpoint will be the proportion of participants who initiate HCV treatment within 12 weeks. Participants who initiate HCV treatment will be traceable, so participants lost to follow-up before initiating HCV treatment will be included in Intention to Treat analyses as having not initiated treatment. Randomised groups will be compared using repeated measures logistic regression methods, clustered on site, fitted using GEE methods with robust standard errors. Secondary analyses will include the proportion linked to care, time to HCV treatment initiation, the proportion initiating HCV treatment by 24 weeks of follow-up, the proportion initiating HCV treatment by the end of follow-up, HCV treatment completion, and response to HCV treatment.

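### Follow-up Visit 1, with its repeat HCV RNA test, can be held from week 10 in intervention participants only, so starts it prompts would count in the 12-week primary outcome

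*Protocol*

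**What the plan says.** Section 14.2 defines the primary outcome as "The proportion who initiate HCV treatment at 12 weeks from enrolment". Section 14.5 restates it: "The primary endpoint will be the proportion of participants who initiate HCV treatment within 12 weeks". Neither section excludes or separates starts that follow a study visit.

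The windows in section 1.3.1 are "Visit Window (weeks, min to max) 0 N/A 10 to 14 14 to 34 34 to 56"; the third entry, weeks 10 to 14, is Follow-up Visit 1. Section 10.5 says that "participants with a quantifiable HCV RNA in the intervention arm only will return for follow-up visits at 12 weeks", and lists questionnaires, an HCV RNA test and reimbursement as the procedures.

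The control schedule (1.3.2) has no visit after registration. Section 10.3 leaves control-phase participants to site standard of care. Section 10.6 lets an untreated control participant be re-screened only once 3 months have passed since screening. Section 8.1, however, ends by saying that all HCV RNA positive participants are followed up at 12 weeks, 24 weeks and 12 months, which conflicts with 1.3.2, 10.3 and 10.5.

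Section 1.3.1 marks result notification at screening and registration and treatment work-up at registration. Neither is marked at Follow-up Visit 1. Sections 9.1 and 10.4 have the date of first dose recorded.

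**The concern.** The hypotheses in section 14.1 attribute any gain in treatment uptake to the testing method. A second study contact, paid and with a repeat RNA test, offered in one arm only and before the outcome closes, is a separate influence on the same outcome. An untreated intervention participant seen in week 10 or 11 can be offered treatment then and start before week 12. A control participant has no matching occasion.

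At stake is the comparison of intervention with standard of care. Any start prompted by the visit adds to the intervention side only, and a larger sample would not remove it. The longer-term comparisons share the feature: the 24- and 52-week initiation proportions (secondary objectives 2 and 3) also accumulate in arms that have scheduled re-tests and are compared with an arm that has none.

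**Working it through.** **Overlap of the windows.** Visit 1 runs from week 10 to week 14, and the outcome closes at week 12 (12 × 7 = day 84). The overlap is 12 − 10 = 2 weeks of a 4-week window, that is, half. For controls the earliest study re-test is at 3 months, about 52 / 4 = 13 weeks, after the outcome has closed.

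**The plan's own figures.** Section 7.1.4 expects 12-week uptake of 10% (control), 20% (dried blood spot) and 45% (point-of-care). With 220 participants each: 220 × 0.10 = 22, 220 × 0.20 = 44 and 220 × 0.45 = 99, total 165. This reproduces section 14.3 exactly.

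**Size of the possible bias.** Let u be the share not yet treated when the visit window opens, a the share of those seen between weeks 10 and 12, and s the share of those seen who start by week 12 because of the visit. Then

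added uptake = u × a × s.

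The protocol gives neither a nor s; both are assumptions. To isolate the artefact, suppose there is no true effect and uptake is 10% in every arm, so u is taken as 0.90. The control arm gains nothing.

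| a | s | Added uptake in intervention | Extra starts per 220 | Approximate chance of a significant result favouring intervention |
|---|---|---|---|---|
| 0.10 | 0.10 | 0.90 × 0.10 × 0.10 = 0.9 points | 2.0 | 0.04 |
| 0.10 | 0.25 | 0.90 × 0.10 × 0.25 = 2.3 points | 5.0 | 0.08 |
| 0.25 | 0.25 | 0.90 × 0.25 × 0.25 = 5.6 points | 12.4 | 0.28 |

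The last column compares 440 intervention with 220 control participants. Sample sizes are divided by the design effect 1 + (20 − 1) × 0.05 = 1.95 (cluster size and ICC from section 14.3), with alpha 0.05 taken as two-sided. The nominal value in that direction is 0.025. It is a parallel-cluster approximation that ignores the within-site part of the stepped wedge, so it shows order of magnitude only. Shares of 0.50 each would give 0.90 × 0.50 × 0.50 = 22.5 points, but nothing in the protocol suggests values that high.

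**Between the two tests.** Two features pull in opposite directions.

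- Re-test results come back faster with point-of-care. Section 10.2 gives same-day notification where possible; for the other arm, "Dried blood spot arm: HCV RNA result will be delivered within two weeks of testing".
- More dried blood spot participants are expected to be untreated: 100% − 20% = 80%, against 100% − 45% = 55%. Equal shares of 0.25 would add 80 × 0.25 × 0.25 = 5.0 points with dried blood spot and 55 × 0.25 × 0.25 = 3.4 points with point-of-care. These are rough, because the expected uptakes are 12-week figures and the formula needs the share unstarted at week 10.

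The net direction cannot be derived.

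**The case against.** The best defence is that Visit 1 is an assessment visit, not a route into treatment. Notification and work-up are not marked there, the turnaround times belong to the initial test, and a start still needs work-up, a prescription and collection from a community pharmacy (sections 9.1 and 10.4), all before week 12. The follow-up questionnaire is an abbreviated one whose items are not listed, so it cannot be said to raise treatment again. A window centred on week 12 is an ordinary choice, and a sensitivity analysis may sit in a statistical analysis plan that was not available here. All of this stands as a reason to expect a modest effect. It does not remove the point, because starts prompted by the visit are not barred, they count, and only one side has the visit.

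A reader might infer three stronger things that the protocol does not support.

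- **That the visit inflates point-of-care over dried blood spot.** Everyone due at Visit 1 already has a quantifiable RNA result, so no new result is needed to start treatment. A dried blood spot participant who never came back could receive the original positive result at that visit.
- **That start dates cannot help afterwards.** First-dose dates are recorded and a case report form is completed for each visit (section 17.1), so starts on or after Visit 1 can be identified and the effect bounded, though cause cannot be proved.
- **That the bias can be sized from the expected uptakes.** Those are 12-week figures, and adding visit-prompted starts to them would risk double counting.

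**Conclusion.** The point holds for intervention versus standard of care. An unequal, reimbursed study contact with a repeat RNA test can fall inside the primary outcome window, and any starts it prompts favour intervention. Its size depends on attendance and start shares that the protocol does not give: about 0.9 points at 0.10 each and 5.6 points at 0.25 each under no true effect, against a planned difference of 20 points in section 14.3. It may be trivial; it is not shown to be large. No bias in a stated direction is claimed for point-of-care versus dried blood spot. The conclusion rests on sections 1.3.2, 10.3 and 10.5 being the intended follow-up rule rather than the last sentence of section 8.1.

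**What to change.** - Open the Visit 1 window no earlier than day 84, for example weeks 12 to 16, and start the Visit 2 window at week 16.
- State in section 14.5 that the primary outcome is scored from the recorded date of first dose. Sections 9.1 and 10.4 already provide it, so no visit before week 12 is needed.
- If follow-up is already under way, prespecify a sensitivity analysis in which starts on or after a Visit 1 held before day 84 do not count as 12-week starts.
- For the 24- and 52-week initiation comparisons with standard of care, state that the intervention arms include scheduled re-testing.
- Reconcile section 8.1 with sections 1.3.2, 10.3 and 10.5 on whether controls are followed up.

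The cost is one schedule row and a few sentences, with no extra participants or visits. The midpoint of the window moves from week 12 to week 14, so the 12-week RNA test (objective 6) and questionnaires are taken up to about two weeks later on average. The visit may also line up less well with an end-of-treatment visit, which the flow chart in section 1.2 allows it to coincide with.
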